6.3. Lifestyle Restrictions

6.3.1. Meals and Dietary Restrictions

- Standard meals will be provided during the study dosing period at specified times that do not interfere with study procedures.
- Study treatment will be taken with food (a meal or a snack) (see Section [7.1](#)).
- Participants will refrain from consumption of Seville oranges, grapefruit, or grapefruit juice (and/or pummelos, exotic citrus fruits, or grapefruit hybrids) from the Baseline Visit through collection of the final PK sample.

6.3.2. Caffeine and Alcohol

- Participants will abstain from ingesting caffeine- or xanthine-containing products (e.g., coffee, tea, cola drinks, and chocolate) from the Baseline Visit through collection of the final PK sample.
- Participants will abstain from alcohol from the Baseline Visit through collection of the final PK sample.

6.3.3. Activity

- Participants will abstain from strenuous exercise for 48 hours prior to each blood collection for clinical laboratory tests during the On-Therapy Visit; participants may engage in light recreational activities during the study (e.g., watch television, read).
- On Days 1 and 4, for the dose associated with serial PK collections, participants should be in a semi-supine position for approximately 3 hours after study treatment administration with only minor exceptions (e.g., urine PK collections). Postdose compliance with a semi-supine position will be recorded in the source documents.

6.4. Screen Failures

Screen failures are defined as participants who consent to participate in the clinical study but are not subsequently entered in the study. A minimal set of screen failure information is required to ensure transparent reporting of screen failure participants to meet the Consolidated Standards of Reporting Trials publishing requirements and to respond to queries from regulatory authorities. Minimal information includes demography, screen failure details, eligibility criteria, and any serious AEs (SAEs).

Participants who are screen failures are not allowed to be rescreened for the same infection episode; however, participants who were screen failures for an earlier infection episode may be newly screened for a later infection episode and participate in the study if they meet all of the inclusion and exclusion criteria.

7. TREATMENTS

Study treatment is defined as any investigational treatment(s), marketed product(s), placebo, or medical device(s) intended to be administered to a study participant according to the study protocol.

7.1. Treatments Administered

Participants will receive oral study treatment (gepotidacin 1500 mg [2 × 750-mg tablets]) BID for 5 days (10 total doses). All doses of study treatment will be administered under site staff supervision in the clinic and all doses will be administered with food (i.e., standardized meals or snacks as applicable). The first dose will be administered at the clinic by 2 PM on Day 1 (for practical reasons and participant convenience) and subsequent doses will be administered approximately every 12 hours. Participants should remain in the clinic to complete a total of 10 doses.

Study Treatment Name:	Gepotidacin
Dosage Formulation:	Tablets containing gepotidacin and inactive formulation excipients
Unit Dose Strengths/Dosage Levels:	750 mg per tablet/1500 mg per dose (2 × 750-mg tablets)
Route of Administration:	Oral
Dosing Instructions:	Administer twice daily for 5 days: 1500 mg – 2 × 750-mg tablets (3000 mg total daily dose) Each dose should be taken after food consumption and with water.
Packaging and Labeling:	Gepotidacin tablets will be provided in bottles. Each bottle will be labeled as required per country requirement.
Manufacturer:	GlaxoSmithKline

7.2. Dose Modification

The study design does not allow for dose modifications.

7.3. Method of Treatment Assignment

This is a nonrandomized, open-label study. Clinic personnel will enroll the participant into the study once a participant has met all eligibility requirements.

7.4. Blinding

This will be an open-label study.

7.5. Preparation/Handling/Storage/Accountability

1. The investigator or designee must confirm appropriate temperature conditions have been maintained during transit for all study treatment received and any discrepancies are reported and resolved before use of the study treatment.
2. Only participants enrolled in the study may receive study treatment and only authorized site staff may supply or administer study treatment. All study treatments must be stored in a secure, environmentally controlled, and monitored (manual or automated) area in accordance with the labeled storage conditions with access limited to the investigator and authorized site staff.
3. The investigator, institution, or the head of the medical institution (where applicable) is responsible for study treatment accountability, reconciliation, and record maintenance (i.e., receipt, reconciliation, and final disposition records).
4. Further guidance and information for the final disposition of unused study treatment are provided in the Study Reference Manual (SRM).

- Under normal conditions of handling and administration, study treatment is not expected to pose significant safety risks to site staff.
- A Material Safety Data Sheet/equivalent document describing occupational hazards and recommended handling precautions either will be provided to the investigator, where this is required by local laws, or is available upon request from GSK.

7.6. Treatment Compliance

- Participants will receive study treatment in the clinic directly from the investigator or designee, under medical supervision. The date and time of each dose will be recorded in the source documents. The dose of study treatment and study participant identification will be confirmed at the time of dosing by a member of the study site staff other than the person administering the study treatment. Study site personnel will examine each participant's mouth to ensure that the study treatment was ingested.

7.7. Concomitant Therapy

Any medication or vaccine (including over-the-counter or prescription medicines, vitamins, and/or herbal supplements) that the participant is receiving at the time of enrollment or receives during the study must be recorded along with:

- Reason for use
- Dates of administration including start and end dates
- Dosage information including dose and frequency

The medical monitor should be contacted if there are any questions regarding concomitant or prior therapy.

7.7.1. Permitted Medications and Nondrug Therapies

The use of H₁ antihistaminics not associated with QT prolongation is allowed (e.g., loratadine, cetirizine, ebastine, and fexofenadine). The use of topical, nonsystemic antibacterials and topical, nonsystemic antifungals is allowed throughout the study.

7.7.2. Prohibited Medications and Nondrug Therapies

At the time of enrollment and/or during the study from the Baseline Visit through the TOC Visit, the participant is prohibited from use of the following medications and nondrug therapies:

- An investigational product within 30 days or 5 half-lives, whichever is longer, of the Baseline Visit.
- Treatment with other systemic antimicrobials or systemic antifungals within 1 week before study entry. Treatment with systemic fluconazole or other systemic antifungals per local standard of care is only allowed after all TOC Visit procedures have been completed.

- Immunosuppressive therapy, including corticosteroid therapy (>40 mg/day prednisolone or equivalent for >1 week or ≥20 mg/day prednisolone or equivalent for >6 weeks; or prednisolone or equivalent ≥10 mg/day for >6 weeks).
- QT-prolonging drugs or drugs with known TdP risk, per the www.crediblemeds.org “Known Risk of TdP” category, at the time of their Baseline Visit, which cannot be safely discontinued from the Baseline Visit to the TOC Visit. Details regarding website access are provided in the SRM.

Note: Crediblemeds.org categorizes drugs into 4 categories. The only category for exclusion in this study is the “Known Risk of TdP” category; participants taking drugs that meet criteria of other categories are NOT excluded from participation.

- Strong CYP3A4 inhibitors (a list of strong CYP3A4 inhibitors is provided in the SRM).
- Strong P-gp inhibitors (a list of strong P-gp inhibitors is provided in the SRM).
- St John’s wort is not permitted from 14 days before study entry through the TOC Visit.
- Prescription, nonprescription, or supplements that may impact UTI clinical or microbiological efficacy outcomes including, but not limited to, *Uva ursi*, cranberry tablets, phenazopyridine, nonsteroidal anti-inflammatory drugs including cyclooxygenase 2 inhibitors, uricosuric drugs (such as probenecid and sulfapyrazone).
- Antacids administration is not permitted within 2 hours before or after study treatment administration.

Due to the gepotidacin’s property of acetylcholinesterase inhibition, the concomitant use of succinylcholine or other nondepolarizing paralytic agents is also prohibited. Caution should be used in participants who have a condition requiring medication that may be exacerbated by acetylcholinesterase inhibition or neuromuscular blocking agents.

7.8. Treatment after the End of the Study

Participants will not receive any additional treatment from GSK after they discontinue or complete the study (i.e., after the Follow-up Visit). Participants experiencing signs and symptoms suggestive of infection recurrence or relapse at the Follow-up Visit will be assessed and treated per the investigator’s judgement.

8. DISCONTINUATION CRITERIA

8.1. Discontinuation of Study Treatment

Participants may voluntarily discontinue study treatment at any time. The investigator may also, at his or her discretion, discontinue the participant from study treatment at any time and initiate appropriate alternative therapy. Reasons for study treatment discontinuation may include the following:

- Adverse event

- Protocol deviation
- Termination of the study by GSK
- Investigator discretion
- Lack of efficacy

Note: Pathogen identification or in vitro resistance of recovered uropathogens is not a reason for study treatment discontinuation.

The reason for study treatment discontinuation will be recorded in the electronic case report form (eCRF). Participants who discontinue study treatment for the reasons above will not be considered withdrawn from the study and should attend the TOC and Follow-up Visits as applicable.

If a participant discontinues during the on-treatment confinement period, Day 5 assessments ([Table 1](#)) will be completed before the participant is discharged. The participant will be instructed to return for the TOC and Follow-up Visits.

8.1.1. Liver Chemistry Stopping Criteria

Liver chemistry stopping and increased monitoring criteria have been designed to assure participant safety and evaluate liver event etiology.

Discontinuation of study treatment for abnormal liver tests is required when:

- a participant meets one of the conditions outlined in [Figure 2](#) and [Figure 3](#).

OR

- when in the presence of abnormal liver chemistries not meeting protocol-specified stopping rules, the investigator believes study treatment discontinuation is in the best interest of the participant.

Figure 2 Liver Chemistry Stopping and Increased Monitoring Algorithm

[figure not shown]
[figure not shown]

Figure 3 Liver Chemistry Increased Monitoring Algorithm with Continued Therapy for ALT ≥ 3 x ULN but < 8 x ULN

For details of the required assessments if a participant meets the above criterion, refer to [Appendix 8](#).

8.1.2. QTc Stopping Criteria

A participant who meets the following bulleted criteria based on the average of triplicate ECG readings will be withdrawn from study treatment:

- QTc >500 msec OR uncorrected QT >600 msec
- Change from baseline of QTc >60 msec

For participants with underlying bundle-branch block, follow the discontinuation criteria listed below:

Baseline QTc with Bundle-Branch Block	Discontinuation QTc with Bundle-Branch Block
<450 msec	>500 msec
450 to 480 msec	≥530 msec

- The *same* QT correction formula *must* be used for *each individual participant* to determine eligibility for and discontinuation from the study. This formula may not be changed or substituted once the participant has been enrolled.
 - For example, if a participant is eligible for the protocol based on QTcB, then QTcB must be used for discontinuation of this individual participant as well.
 - Once the QT correction formula has been chosen for a participant's eligibility, the same formula must continue to be used for that participant *for all QTc data being collected for data analysis*. Safety ECGs and other non-protocol specified ECGs are an exception.
- The QTc should be based on averaged QTc values of triplicate ECGs obtained over a brief (e.g., 5- to 10-minute) recording period.

See [Table 1](#) for data to be collected at the time of treatment discontinuation and follow-up and for any further evaluations that need to be completed.

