3.3.1. Risk Assessment

Potential Risk of Clinical Significance	Summary of Data/Rationale for Risk	Mitigation Strategy
Gepotidacin (e.g., GSK2140944)		

Cardiovascular Effects
 
Based on nonclinical data, cardiovascular effects were reversible increase in heart rate and blood pressure (dog and monkey); reversible 10 to 21 msec (4% to 9%) increase in QTc (monkey); and at the highest dose, a reversible 2 to 3 msec (6% to 8%) increase in QRS (monkey).
 
Based on a thorough QTc clinical study, gepotidacin may cause mild, reversible heart rate effects and QT prolongation.
	
In a thorough QTc study, infusion of gepotidacin at doses of 1000 and 1800 mg over 2 hours caused a mild increased heart rate effect of approximately 6 to 10 bpm and QT prolongation measured as $\Delta\Delta$QTcF of 12 to 22 msec. The QT prolongation evolved during the infusion and was quickly reversed over 2 hours after the end of the infusion (see Section 5.2.6 and Section 6 of the IB).
 
No changes in QRS or QTc of clinical concern have been seen in the clinic (Phase I studies and Phase II ABSSSI study) (see Section 6 in the IB). Cardiovascular events reported in the Phase II urogenital gonorrhoea study were ECG ST segment elevation and palpitations (1 participant each) in the 1500-mg treatment group and tachycardia (1 participant) in the 3000-mg treatment group.
	
See Section 6.2 for excluded cardiac conditions. Close monitoring of clinical parameters and AEs (Table 1) will be conducted, and treatment monitoring and evaluation criteria (Section 8.1.2) will be utilized to mitigate cardiovascular effects.
 
As a consequence, participants taking QT-prolonging drugs or strong CYP3A4 inhibitors and/or strong P-gp inhibitors will be excluded.

Potential Risk of Clinical Significance	Summary of Data/Rationale for Risk	Mitigation Strategy

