20. The participant has a recent history of vasovagal syncope or episodes of symptomatic bradycardia or bradyarrhythmia within the last 12 months.
21. The participant is taking QT-prolonging drugs or drugs known to increase the risk of torsades de points (TdP) per the www.crediblemeds.org "Known Risk of TdP"

category at the time of her Baseline Visit, which cannot be safely discontinued from the Baseline Visit to the TOC Visit; or the participant is taking a strong cytochrome P450 enzyme 3A4 (CYP3A4) inhibitor or a strong P-glycoprotein (P-gp) inhibitor.

Cardiac ECG Exclusion

22. The participant has a QTc >450 msec or a QTc >480 msec for participants with bundle-branch block. **Note:** The QTc is the QT interval corrected for heart rate according to either Bazett or Fridericia formula, machine, or manual overread.

Hepatic Exclusions

23. The participant has a known alanine transferase (ALT) value >2 × upper limit of normal (ULN).
24. The participant has a known bilirubin value >1.5 × ULN (isolated bilirubin >1.5 × ULN is acceptable if bilirubin is fractionated and direct bilirubin <35%).
25. The participant has a current or chronic history of liver disease, or known hepatic or biliary abnormalities (with the exception of Gilbert's syndrome or asymptomatic gallstones), including symptomatic viral hepatitis or moderate-to-severe liver insufficiency (Child Pugh class B or C). **Note:** Participants with asymptomatic viral hepatitis are eligible for study participation.

Prior Antibiotic/Antifungal Use Exclusion

26. The participant has received treatment with other systemic antimicrobials or systemic antifungals within 1 week before study entry.

Concomitant Medication Use Exclusion

27. The participant must agree not to use the medications or nondrug therapies from the Baseline Visit through the TOC Visit as detailed in Section [7.7.2](#).

Prior/Concurrent Clinical Study Experience

28. The participant has been previously enrolled in this study or has previously been treated with gepotidacin.
29. The participant has participated in a clinical trial and has received an investigational product within 30 days or 5 half-lives, whichever is longer.

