9.4.3. Electrocardiograms

- Triplicate 12-lead ECGs will be performed at Baseline and single 12-lead ECGs will be performed at other time points as indicated in [Table 1](#) and [Table 2](#) using an ECG machine that automatically calculates the heart rate and measures PR, QRS, QT, and QTc intervals. Refer to [Section 8.1.2](#) for QTc withdrawal criteria and additional QTc readings that may be necessary.
- Electrocardiograms will be obtained in semi-supine position.

- Electrocardiograms should be obtained before any vital sign measurements or blood draws scheduled on the same assessment day.
- For triplicate ECGs, 3 individual ECG tracings should be obtained as closely as possible in succession, but no more than 2 minutes apart. The full set of triplicates should be completed in less than 4 minutes.
- If additional ECGs are performed, clinically significant changes occurring during the study will be reported as AEs.
- Refer to Section 8.1.2 for QTc withdrawal criteria and additional QTc readings that may be necessary.

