12.9.7. Safety Tables

Safety: Tables					
No.	Population	IDSL / Example Shell	Title	Programming Notes	Deliverable
Adverse Events (AEs)					
3.1.	Safety	AE5B	Summary of Adverse Events by System Organ Class and Preferred Term and Maximum Grade		DS, SAC
3.2.	Safety	AE5B	Summary of Drug-Related Adverse Events by System Organ Class and Preferred Term and Maximum Grade		DS, SAC
3.3.	Safety	AE15	Summary of Common (>=5%) Non-serious Adverse Events by System Organ Class and Preferred Term (Number of Subjects and Occurrences)		DS, SAC
Laboratory					
3.4.	Safety	LB1	Summary of Clinical Chemistry Values Change from Baseline		DS, SAC
3.5.	Safety	LB1	Summary of Hematology Change from Baseline		DS, SAC
3.6.	Safety	UR3	Summary of Urinalysis Dipstick Results		DS, SAC
ECG					
3.7.	Safety	EG1	Summary of ECG Findings		DS, SAC
3.8.	Safety	EG10	Summary of Maximum QTc Values Post-Baseline Relative to Baseline by Category		DS, SAC
3.9.	Safety	EG11	Summary of Maximum Increase in QTc Values Post-Baseline Relative to Baseline by Category		DS, SAC
3.10.	Safety	EG2	Summary of Change from Baseline in ECG Values		DS, SAC

Safety: Tables					
No.	Population	IDSL / Example Shell	Title	Programming Notes	Deliverable
Vital Signs					
3.11.	Safety	VS3	Summary of Worst Case Vital Signs Results Relative to Potential Clinical Importance Criteria Post-Baseline Relative to Baseline		DS, SAC
3.12.	Safety	VS1	Summary of Change from Baseline in Vital Signs		DS, SAC

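### The QTc correction formula for analysis is fixed participant by participant and the SAP names none, so the QTc safety tables may mix Bazett and Fridericia values or rest wholly on Bazett

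*Protocol*

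**What the plan says.** **Choice of formula.** Protocol 6.2, exclusion 22, defines QTc as "corrected for heart rate according to either Bazett or Fridericia formula, machine, or manual overread". No single formula is set for the study.

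**Carry-forward.** Protocol 8.1.2 ties discontinuation to the formula used for that participant's eligibility and then widens the rule: "the same formula must continue to be used for that participant", and this holds "for all QTc data being collected for data analysis". It is therefore an analysis rule as well as a stopping rule. There is one carve-out: "Safety ECGs and other non-protocol specified ECGs are an exception".

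**SAP displays.** SAP 12.9.7 lists Table 3.8, "Summary of Maximum QTc Values Post-Baseline Relative to Baseline by Category", Table 3.9 on the largest QTc increase, and Table 3.10 on change from baseline in ECG values. SAP 12.6.1 gives one set of QTc cut-offs: 450, 480 and 500 msec for level, 30 and 60 msec for increase. None of these names a formula, splits by formula or re-derives QTc. The SAP's table of changes from the protocol (section 2.1) does not mention QTc.

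**Unscheduled ECGs.** SAP 12.3.2 keeps unscheduled visits out of summaries except where they determine the baseline or the worst-case value.

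**Known drug effect.** Protocol 3.3.1 reports that infusion of 1000 and 1800 mg over 2 hours "caused a mild increased heart rate effect of approximately 6 to 10 bpm", and gives the QT effect on the Fridericia scale: a double-delta QTcF of 12 to 22 msec.

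**The concern.** Bazett and Fridericia agree only at 60 bpm and move apart as heart rate rises. If the formula varies between participants, a mean or category count labelled QTc depends partly on how many women happened to be screened on each formula. If the site uses Bazett throughout, the tables are consistent with one another, but every change carries a heart-rate component that the programme's QTcF data do not.

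The carve-out for safety and non-protocol ECGs adds a second route. Those tracings may use another formula, yet unscheduled readings feed the worst-case values. Tables 3.8 and 3.9 could then compare a baseline on one scale with a maximum on the other within the same woman.

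What is at stake is how the QTc safety summaries can be read, for a drug that the protocol says may prolong QT and raise heart rate. Nothing in the PK analysis depends on it.

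**Working it through.** The plan states no QTc figure to reproduce, so the check is the algebra of the two formulas, using the protocol's heart-rate effect.

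**Inputs**
- Heart-rate rise: +6 to +10 bpm (Protocol 3.3.1, intravenous infusion).
- QTcF rise, as an illustration: 12 and 22 msec (the ends of the range in Protocol 3.3.1; there a double-delta, here used only as plausible individual changes).
- Baseline heart rate 60 to 90 bpm and baseline QTcF 390 to 430 msec: assumptions, not in the documents.

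**Formula.** With RR = 60/HR, QTcB = QT/RR^(1/2) and QTcF = QT/RR^(1/3). Hence QTcB = QTcF × (HR/60)^(1/6).

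**Difference in level, QTcF 410 msec**

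| Heart rate (bpm) | QTcB − QTcF (msec) |
|---|---|
| 60 | 0 |
| 70 | 10.7 |
| 80 | 20.1 |
| 90 | 28.7 |

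A QTcF of 430 msec reads as a QTcB of 450 msec at 60 × (450/430)^6 = 78.8 bpm, so the formula alone can decide the 450 msec category.

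**Change on Bazett when QTcF does not change**
- QTcF 410, 70 to 76 bpm: 410 × [(76/60)^(1/6) − (70/60)^(1/6)] = 426.5 − 420.7 = 5.8 msec.
- QTcF 410, 70 to 80 bpm: 430.1 − 420.7 = 9.5 msec (from unrounded values).
- Over the whole assumed baseline range: 4.5 to 6.9 msec for +6 bpm and 7.4 to 11.2 msec for +10 bpm. The smallest values are at QTcF 390 and 90 bpm, the largest at QTcF 430 and 60 bpm.

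**Change on Bazett when QTcF also rises (baseline 410 msec, 70 bpm)**
- +12 msec and +6 bpm: 422 × (76/60)^(1/6) − 420.7 = 18.3 msec.
- +22 msec and +10 bpm: 432 × (80/60)^(1/6) − 420.7 = 32.5 msec. Over the assumed range this is 31.3 to 33.8 msec, always above 30 msec, while the QTcF change is 22 msec.

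**Effect on the >30 msec category.** This illustration uses assumed normal distributions: QTcF 410 (SD 15), heart rate 70 (SD 8), SD of QTcF change 8 to 12, SD of heart-rate change 5.

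| Mean change | Share >30 msec, Fridericia | Share >30 msec, Bazett |
|---|---|---|
| 12 msec, +6 bpm | 1% to 7% | 11% to 19% |
| 22 msec, +10 bpm | 16% to 25% | 57% to 60% |

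A mixed table would fall between the two columns, at a point set by an unknown share of participants on each formula. With 25 to 30 women enrolled (Protocol 5.2), each reclassified participant moves a percentage by 1/30 = 3.3 to 1/25 = 4 points.

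**The case against.** **Mixing is permitted, not shown.** This is a single-centre study, and Protocol 9.4.3 describes a machine that "automatically calculates the heart rate and measures PR, QRS, QT, and QTc intervals". One site may use one formula throughout. This stands: a reader might infer that the tables will pool two scales, and the documents do not establish that. It does not remove the point. Uniform Bazett would still put the heart-rate component into every change; only uniform Fridericia avoids the problem, and nothing in the plan requires it.

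**Unseen standards.** SAP 8.3 refers ECG analyses to the sponsor's core data standards, which may display QTcB and QTcF separately. That is possible, but they would have to override an explicit protocol rule, and the SAP does not say that they do.

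**The heart-rate input is borrowed.** The 6 to 10 bpm comes from infusion; here tablets are taken with food. Protocol 3.3.1 also reports no QTc changes of clinical concern in Phase I or in the Phase II skin-infection study. This stands, so the size is conditional.

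**Comparison with the thorough QTc study.** A reader might infer that switching to QTcF would isolate the drug effect or allow direct comparison with the 12 to 22 msec. It would not. That figure is a double-delta, whereas this study has one arm and reports an uncontrolled change from baseline. A common formula removes one source of difference only.

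**Which formula is right.** The documents do not say that Bazett over-corrects. The added milliseconds are relative to Fridericia, which is the scale the protocol itself uses for this drug's QT effect.

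**Consistency within a participant.** Her scheduled values stay on one formula. This is true of scheduled ECGs, but not necessarily of the exempt tracings that can enter Tables 3.8 and 3.9.

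**Conclusion.** The point holds as a defect in the stated analysis rule. The protocol carries an individually chosen formula into the analysis data, and the SAP neither names a formula nor brings the values to a common one. The tables may therefore mix scales across participants, sit wholly on Bazett, or mix formulas within a participant through unscheduled ECGs.

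The size is 4.5 to 6.9 msec for +6 bpm and 7.4 to 11.2 msec for +10 bpm on a Bazett change relative to Fridericia. It rests on the assumed baselines and on the intravenous heart-rate effect carrying over to the oral regimen. That is enough to change counts in the >30 msec category.

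No figure for the inflation of the pooled mean can be supported, because the share of women on Bazett is unknown. The affected outputs are descriptive secondary safety tables with no hypothesis test. The change should be made, but it does not threaten the study's main purpose.

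**What to change.** State in the SAP (sections 8.3 and 12.6.1, and the notes to Tables 3.8 to 3.10) that every QTc summary, category and change from baseline uses QTcF. It should be derived for each participant and time point, unscheduled ECGs included, from the recorded QT and heart rate. Show QTcB only in a supplementary listing.

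Because this departs from the analysis clause of Protocol 8.1.2, add an entry with a rationale to the SAP's table of changes from the protocol. Leave the per-participant formula rule for eligibility and individual discontinuation unchanged.

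The cost is a few lines of SAP text and one derived variable. The ECG machine already produces QT and heart rate; the one thing to confirm is that both reach the database for every tracing, unscheduled ones included.
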